In order to visualize the distribution of TTFIELDS in the tumor and the surrounding brain tissues, the coupled Maxwell equations must be solved using numerical approximations such as finite element modeling. These computer modeling procedures involve the segmentation of various brain tissues as seen on patient MRI datasets, the application of appropriate initial and boundary conditions and material properties and finding the solution to the coupled Maxwell equations using finite element analysis. A heatmap of the electric field distribution within the human brain can be derived as well as the electric field-volume and specific absorption ratio-volume histograms can be constructed [73]. From these histograms, the electric field parameters, including E_{AUC} , E_{V150} , $E_{95\%}$ and $E_{50\%}$, as well as specific absorption ratio parameters, including SAR_{AUC} , $V_{SAR7.5}$, $SAR_{95\%}$ and $SAR_{50\%}$, can then be used to compare the dosage applied to different patients. Past effort has shown that the electric field strength estimated by computer modeling was within 10% of that measured directly [45]. However, aggregate analysis is lacking on a larger homogeneous patient population that has been treated by TTFIELDS. Therefore, in this protocol, we will perform computer modeling of electric field and energy deposition in the tumor and then perform correlative analysis with respect to overall survival, progression-free survival and response.

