6.3.2.2 MRI Acquisition and DICOM images

The process of numerical estimation of electric field strength at the gross tumor volume consists of a number of steps. First, gadolinium-enhanced MP RAGE sequences will be acquired using MRI in one axis and reconstructed in the other two axes resulting in axial, coronal and sagittal images. Standard T2, FLAIR and pre-gadolinium sequences will also be obtained per local care standards. The field of view of the images should include the surface of the scalp (Fig. 7). These images will be exported as DICOM images.

Second, the DICOM images will be imported into a tissue segmentation software program as previously described [69]. Third, both intracranial and extracranial structures, including scalp, skull, dura, cerebrospinal fluid, gray matter, white matter and bilateral ventricles, will be segmented and meshed before solving using finite element methods [62].

Lastly, the electric field strength and the specific absorption ratio at the gross tumor volume will be tabulated using various electric field strength parameters, including EAUC, EV150, E95% and E50%, and specific absorption ratio parameters, including SARAUC, VSAR7.5, SAR95% and SAR50%. Together, these parameters will allow the comparison among patients of the electric field strength, as well as the amount of energy deposited, at the tumor.

The electric field and specific absorption ratio parameters will be correlated with measures of clinical outcome, including response rate, progression free survival and overall survival. Spearman rank-order correlation will be performed between the non-parametric electrical and clinical outcome variables.

The DICOM images will be obtained for analysis at baseline, each two months per protocol, and at the time of first and second progression. These analyses will be performed at Beth Israel Deaconess Medical Center. Analysis will be completed within two years of the last patient's enrollment.

[figure not shown]

Figure 7. MRI image samples demonstrating field of view of the images must include the surface of the scalp. Incorrect image on the left does not include full scalp surface where indicated by arrows. The correct image at the right does include the surface of the scalp around the entire head.

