10.2.1 Analysis of Primary and Secondary Endpoints and Correlative Studies

We will compare OS and progression-free survival (PFS) between historical control and experimental treatment arms using the log-rank test (we will also collect PFS data via chart review for the historical control patients). For our correlative studies, we will use the independent-sample t test to compare mean mutation burden between patient samples treated with RT+temozolomide or RT+temozolomide+TTFields. We may perform the same comparison within a linear regression framework if the need arises to adjust for any potential confounders for the effect of TTFields in our correlative studies.

To investigate the influence of electric field and energy deposition in the tumor on outcomes, we will use the Wilcoxon rank sum test to compare the electric field and specific absorption ratio parameters between: responders and non-responders; subjects with progression-free survival \geq and $<$ 1 year; subjects with overall survival \geq and $<$ 2 years; and subjects with overall survival \geq and $<$ 1.5 years. We will estimate Pearson correlation coefficients to assess the correlation of OS and PFS with electric field or specific absorption ratio parameters.

We may stratify the patients by MGMT methylation status, extent of resection, or a combination of the two.

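### The exploratory electric-field dose-outcome analysis cuts OS and PFS for Wilcoxon tests and correlates uncut times without handling censoring; a Cox model on the same data would be more powerful

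*Combined protocol and SAP*

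**What the plan says.** Section 2.1.2.6.2 gives the lack of an aggregate analysis in a larger homogeneous population as the reason for modeling field and energy deposition, and says the study will "perform correlative analysis with respect to overall survival, progression-free survival and response". Table 2 lists the modeling under tertiary/exploratory endpoints. Section 9.5 leaves controls out of the MRI correlative study, so only treated patients contribute.

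Two sections describe the statistics.

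- **Section 10.2.1:** "we will use the Wilcoxon rank sum test to compare the electric field and specific absorption ratio parameters between: responders and non-responders". The same test is then applied to three survival splits: PFS at 1 year, OS at 2 years and OS at 1.5 years. The next sentence adds: "We will estimate Pearson correlation coefficients to assess the correlation of OS and PFS with electric field or specific absorption ratio parameters".
- **Section 6.3.2.2:** for the same parameters and outcomes, "Spearman rank-order correlation will be performed between the non-parametric electrical and clinical outcome variables". It lists eight parameters, four for field strength and four for specific absorption ratio.

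No Cox or other censored-data regression is named for this analysis. Nothing is said about censored times, the choice of cuts, the significance level, the effect size or power.

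**The concern.** A cut turns a survival time into a yes/no label. With the 2-year cut, a death at month 1 counts the same as one at month 23, and a death at month 25 the same as survival to month 60. OS is cut twice, which adds tests but no new information. With eight parameters and three cuts there are 8 x 3 = 24 cut-point tests, where one Cox model per parameter and endpoint would need 8 x 2 = 16.

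The correlations avoid the cut but, as written, would have to use a censored time as if it were a death or progression time. The two sections also name different coefficients for one purpose.

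At stake is whether the study can answer the question in Section 2.1.2.6.2. A real, moderate relation between field dose and outcome could be missed by tests that use only part of the data.

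**Working it through.** **Inputs from the protocol (Sections 10.1 and 10.2).** Treated N = 90; accrual 36 months; follow-up 24 months after accrual, so administrative censoring falls between 24 and 60 months; Weibull survival with shape k = 2.0 (1.8 also considered); control median OS 22 months. A treated median of 28 (22 + 6) was also run.

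**Assumptions, because the documents give no figure.** Hazard ratio (HR) per SD of a field parameter; two-sided 0.05; median PFS 6.7 months (borrowed from the GBM trial in Section 2.1.2.4) to 12 months; field parameter standard normal; no loss to follow-up unless stated.

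**Step 1: check the survival model against Table 10.** Event probability = 1 - (1/36) x integral from 24 to 60 of exp(-ln 2 x (c/median)^k) dc. For k = 2 this is 0.871 at median 22 and 0.751 at median 28.

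- Events = 90 x (0.871 + 0.751) = 146.0.
- HR = (22/28)^2 = 0.617, and ln HR = -0.482.
- One-sided power = Phi(sqrt(146.0/4) x 0.482 - 1.645) = Phi(1.27) = 0.898.

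Table 10 gives 0.894 for 90+0 controls and 6 months. The other gains in that row, and the k = 1.8 row with 90 controls, also agree within 2 points, so the model is a fair base.

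**Step 2: simulate the field analysis.** The hazard is Weibull(k, median) x exp(x ln HR), with x the field parameter and censoring uniform on 24 to 60 months. The same data sets were analyzed by a Cox test on x, by a Wilcoxon test of x across the cut, and by Pearson and Spearman correlation of x with the observed time. Each scenario had 1,500 to 4,000 simulated trials, and independent runs differed by about 2 points. Power at HR 0.75 per SD:

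| Endpoint | Cox | Pearson, uncut | Wilcoxon at cut |
|---|---|---|---|
| OS, median 22, k = 2 | 69% | 61% | 47% (2 years), 35% (1.5 years) |
| OS, median 28, k = 2 | 63% | 51-53% | 37-38% (2 years), 25-27% (1.5 years) |
| PFS, median 6.7, k = 1 | 72-74% | 70-72% | 51-52% |
| PFS, median 12, k = 1 | 70% | 65-67% | 43% |
| PFS, median 12, k = 2 | 72% | 68% | 43% |

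**Step 3: vary the effect size.** Loss of the cut tests against Cox:

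- HR 0.80: about 16 to 27 points for OS.
- HR 0.75: about 22 to 38 points for OS, and about 20 to 29 for PFS.
- HR 0.70: about 20 to 43 points for OS.
- HR 0.50: about 1 to 10 points, because nearly every test succeeds.
- HR 0.85: about 10 to 16 points, because no test has much power.

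At HR 0.72, where Cox has about 80% power at median 22, the losses are 38 points (1.5-year cut) and 23 points (2-year cut). Testing one-sided at 0.05 instead gives losses of about 16 to 40 points at that HR.

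**Step 4: compare with the planned correlations.** With complete follow-up, Pearson is about 2 to 13 points below Cox at HR 0.75. Spearman for OS is about 13 to 16 points below. If 10% are lost by 24 months (assumed), Pearson for OS falls to 51% against Cox 65% at median 22, and to 41% against 58% at median 28. Those gaps are 14 and 17 points, and about 13 to 20 across runs. About 8% of patients would then have unknown 2-year status, and the plan has no rule for them.

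**Step 5: null case.** With no field effect and complete follow-up, all four tests reject at about 5%. The difference is in power, not false positives.

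**The case against.** The strongest reply is that the cut tests are only part of the plan. Section 10.2.1 correlates the uncut times in the very next sentence, and Pearson recovers most of the lost power when follow-up is complete. A reader might infer from the Wilcoxon figures that the planned analysis as a whole gives up 20 to 40 points. It does not: that figure belongs to the cut tests alone. Nor does any section say that a non-significant Wilcoxon result will be taken as no relation.

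The effect size is also assumed, and so are the PFS medians. This stands, and it is why the loss can be given only as a conditional range.

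Two further readings are tempting but unsupported.

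- **Late enrollees cannot be classed at 2 years.** Follow-up runs 24 months past the end of accrual, so every patient not lost or withdrawn can be classed at 1, 1.5 and 2 years. Sections 7.2 and 7.3 provide for withdrawal and loss, but no rate is given.
- **The imaging deadline forces an early data cut.** Section 6.3.2.2 says "Analysis will be completed within two years of the last patient's enrollment". With 36 months of accrual that falls at month 60, when data collection is also expected to end (Section 11.1.9.2). Any earlier cut would be invented, and the sentence can be read as covering only the field modeling.

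Finally, the endpoint is exploratory. That limits the weight of the point but does not remove it, because the change needs no new data.

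**Conclusion.** The point holds as a minor improvement to an exploratory analysis. The plan cuts OS twice and PFS once without a stated reason, names two different correlations, and gives no handling of censoring for any of them.

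Under the protocol's survival assumptions, an assumed HR of 0.70 to 0.80 per SD and two-sided 0.05, the OS cut tests lose about 16 to 43 points of power against Cox. Against Pearson, the fairer comparison for the plan as a whole, Cox gains about 2 to 13 points, or about 13 to 20 for OS if 10% are lost by 24 months. These ranges rest on a log-linear field effect, proportional hazards and censoring unrelated to the field parameter. The primary OS comparison is unaffected.

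**What to change.** 1. **Section 10.2.1:** make Cox regression of OS and of PFS on each continuous baseline field or absorption parameter the dose-outcome analysis. Use full follow-up and ordinary censoring, and report the HR per SD with its 95% CI. This replaces the three survival-cut Wilcoxon tests and the Pearson correlations with OS and PFS.
2. **Section 6.3.2.2:** replace the Spearman sentence for OS and PFS with a reference to the same Cox analysis. Otherwise the conflict between the two sections remains.
3. Keep the Wilcoxon test for responders versus non-responders.
4. Show 1.5- and 2-year OS and 1-year PFS descriptively only, as Kaplan-Meier estimates by level of the parameter (tertiles, for example).

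The cost is a few lines of text, with no new patients, data or procedures. The downside is that Cox assumes proportional hazards and a log-linear effect. Both should be checked, with residuals and a spline. Section 10.1 already assumes proportional hazards for survival in the sample-size work.

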
4) Optune therapy should start within two weeks of start of adjuvant temozolomide, but not more than 7 weeks from the end of temozolomide/RT and will be continuous throughout study. Compliance documentation will be obtained every 4 weeks +/- 7 days.
							

5) Every 3 months until death. The only data required during survival follow-up is DOD.
							

6) Biochemistry panel will include electrolytes, creatinine, bilirubin, liver enzymes.
							

7) Patients will begin treatment with temozolomide at 4 weeks (+14 days) from end of radiotherapy. Cycle 1 will be dosed at 150mg/m² daily for 5 consecutive days of a 28-day cycle.
							

Study Procedure:	Screening ≤14 days prior to Day 0	Day 0 : Begin TMZ Treatment	Week 4 (-3/+7 days) and every 4 weeks until treatment stop	Week 8 (±7 days) and every 8 weeks only until treatment stop	Progression	After Treatment Stop (Week 4 (+/- 7 days) from end of treatment)	Survival follow-up

8) Patients will begin treatment with temozolomide Cycle 2 and subsequent cycles every 4 weeks (-3/+7 days) at 200mg/m² PO daily for 5 consecutive days, if CTC hematologic toxicity for cycle 1 is grade < 1 and the CTC non-hematologic toxicity for cycle 1 is grade ≤ 2. If dose escalation is not appropriate, the dose should remain at 150 mg/m² PO daily for 5 consecutive days for Cycle 2 and onward.
							

9) Verification of tissue availability and location should be determined at screening visit. When available, formalin fixed and paraffin embedded (FFPE), pathology slides and/or frozen samples will be obtained for primary tumors and first recurrent tumors.
							

10) Labs to be completed within 3 days for pre-TMZ cycles. Screening and other labs are within the visit windows noted. Pregnancy Test required for WOCBP only at Screening.
							

11) DICOM images will be shipped to Beth Israel Deaconess Medical Center for electric field mapping analysis at baseline, first progression and second progression. Imaging performed between shipping time points should be included in the next shipment.
							

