3 OBJECTIVES AND ENDPOINTS

TABLE 2: OBJECTIVES & ENDPOINTS

OBJECTIVES	ENDPOINTS	JUSTIFICATION FOR ENDPOINTS
Primary		
To determine whether TTFIELDS combined with adjuvant temozolomide increases OS in patients with newly diagnosed Grade II and III astrocytoma with TERT promoter mutation only compared to historical and contemporaneous controls.	OS measured in days from Study Day 0 until death. If the study ends and the participant is still living, OS will be measured in days from Study Day 0.	OS remains the primary concern within this patient population. Intent to Treat analysis will be used to determine if this objective is met.
Secondary		

 To determine whether the combination of TTFIELDS and adjuvant temozolomide is safe in the newly diagnosed high-risk Grade II and III astrocytoma. To determine whether TTFIELDS combined with adjuvant temozolomide increases PFS in patients with newly diagnosed Grade II and III astrocytoma with TERT promoter mutation only compared to historical and contemporaneous controls. To evaluate QOL using KPS, EORTC QLQ-C30/BN20, and MMSE in patients treated with TTFIELDS combined with adjuvant temozolomide compared to 	
 PFS measured in days from Day 0 to progression Safety measured by incidence and severity of Adverse Events and Toxicities. Quality of life measured by KPS, EORTC QLQ-C30/BN20, and MMSE Correlation between % Compliance with TTFIELDS and OS 	Safety, Efficacy, and Quality of Life measures for a more complete view of the effects of the study treatment(s).

historical and contemporaneous controls.		
Tertiary/Exploratory		

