
 • To determine whether the addition of TTFIELDS to adjuvant temozolomide significantly increase mutation burden, compared to historical and contemporaneous controls. • To determine whether TTFIELDS increases immune cell infiltration. • To determine whether TTFIELDS induces immunogenic cell death in tumor. 	
 • Mutation burden before and after TTFIELDS, compared to historical and contemporaneous controls • Immune cell infiltration before and after TTFIELDS, compared to historical and contemporaneous controls • Immunogenic cell death marker before and after TTFIELDS, compared to historical and contemporaneous controls • Computer modeling of electric field and energy deposition 	To add key immunological and mutational information to the information about these specific tumors.

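### Sections 10.2.1 and 6.3.2.2 name different correlation coefficients for the same exploratory field/SAR question, and neither handles censored OS and PFS times

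*Combined protocol and SAP*

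**What the plan says.** Section 10.2.1: "We will estimate Pearson correlation coefficients to assess the correlation of OS and PFS with electric field or specific absorption ratio parameters". It also plans Wilcoxon rank sum comparisons of the same parameters by response, by PFS split at 1 year, and by OS split at 1.5 and 2 years.

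Section 6.3.2.2 correlates the same parameters with response rate, PFS and OS: "Spearman rank-order correlation will be performed between the non-parametric electrical and clinical outcome variables". Neither section refers to the other, ranks the two methods or mentions censoring.

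Section 6.3.2.2 names eight parameters, "including EAUC, EV150, E95% and E50%, and specific absorption ratio parameters, including SARAUC, VSAR7.5, SAR95% and SAR50", without a lead. On timing it says "The DICOM images will be obtained for analysis at baseline, each two months per protocol, and at the time of first and second progression", and footnote 11 of the Schedule of Activities adds "Imaging performed between shipping time points should be included in the next shipment". No section says which scan supplies the value to be analysed.

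Table 2 (section 3) places "Computer modeling of electric field and energy deposition" in its tertiary/exploratory row. Its secondary row includes "Correlation between % Compliance with TTFIELDS and OS". The synopsis lists only PFS, safety and quality of life as secondary endpoints, and section 10 does not mention compliance.

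**The concern.** A Pearson or Spearman coefficient needs a complete value for each patient. For a patient alive at study end, the recorded time is only a lower bound on survival. Entering it as if it were the survival time pulls the association towards zero, and dropping living patients is worse. A real relation between delivered field and outcome becomes easier to miss. With two coefficients named, the choice between them can also be made after the results are seen.

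At stake is the exploratory field-modelling result, which section 2.1.2.6.2 presents as filling a gap in aggregate data. The compliance endpoint raises a related issue: it is listed but has no analysis, and a plain correlation with OS would meet the same censoring problem.

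**Working it through.** **Inputs (sections 10.1 and 10.2).** Experimental arm N = 90; accrual 36 months; follow-up 24 months after the end of accrual; control median OS 22 months; improvements of 4-8 months; Weibull shape k = 2.0 or 1.8. With uniform entry, each patient's potential follow-up is uniform on 24-60 months.

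**Check of the survival model against Table 10.** The plan gives no figure for the correlations, so I first reproduced its log-rank power for 90 + 90 patients, k = 2 and a 6-month gain.
- HR = (22/28)² = 0.617, so |ln HR| = 0.482.
- Expected deaths: 67.6 (experimental) + 75.1 (control, assuming follow-up uniform on 20-60 months) = 142.6.
- Power = Φ(√(142.6 × 0.25) × 0.482 − 1.645) = Φ(1.235) = 0.892, against 0.894 in Table 10. The 45 cells checked all agree within 0.003.

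**Share of OS times censored at study end.** Share = (1/36) ∫ from 24 to 60 of exp(−ln 2 · (t/m)^k) dt, where m is the median.

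| Median OS (months) | k = 2.0 | k = 1.8 |
|---|---|---|
| 22 (no benefit) | 12.9% | 15.0% |
| 26 | 20.8% | 22.9% |
| 28 | 24.9% | 26.9% |
| 30 | 29.1% | 30.8% |

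With a benefit of 4-8 months this is about 19 to 28 of 90 patients. Loss to follow-up would add to it. For PFS the same integral gives 0-2% at the 6.7-month GBM median in section 2.1.2.4 and 1-11% at an assumed 12 months (k from 2 down to 1).

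**Effect on power.** Simulation with 6,000 runs, N = 90, k = 2, a standard-normal parameter and an assumed log-hazard of 0.3 per SD. Tests are two-sided at 5%, also an assumption because the plan sets no level. Observed times are used as OS.

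| Median OS | Pearson | Spearman | Cox |
|---|---|---|---|
| 22 | 64% | 59% | 72% |
| 28 | 56% | 52% | 67% |
| 30 | 52% | 48% | 64% |

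Mean Pearson r falls from about 0.27 without censoring to 0.24/0.22/0.21. At a log-hazard of 0.2, power at the three medians is 36/29/27% (Pearson), 32/27/25% (Spearman) and 42/37/34% (Cox). At 0.4 it is 87/78/75%, 82/75/72% and 91/88/86%.

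**How much of the gap is due to censoring.** The same model without censoring gives about 74% (Pearson), 64% (Spearman) and 77% (Cox).
- Pearson trails Cox by about 2-4 points without censoring and 8-12 with it. Most of its gap is due to censoring.
- Spearman trails Cox by about 12-13 points without censoring. Censoring adds at most about 3. Most of its gap is the inefficiency of ranks under this model.

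**False positives.** With no association, each coefficient rejects at about 5%. Reporting whichever of the two is significant gives 6-7%.

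**Compliance-OS, no device effect.** Assumptions: percent use normal with mean 0.75 and SD 0.12, averaged over time on device; device capped at 24 months; Spearman with observed OS; medians 28 and 22. With no decline in wear, false positives are 4-6%, even if the device stops up to 6 months before death. If wear halves over the last 3 months of life, the rate depends on when the device stops:

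| Device stops | False positives |
|---|---|
| At death | 92-99% |
| 1 month before death | 75-92% |
| 2 months before death | 40-60% |
| 3 months before death | 6-9% |

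**The case against.** The case on the other side is that field modelling is exploratory, that 10.2.1 names the Wilcoxon comparisons first, and that the primary analysis is untouched. All of this stands. The splits at PFS 1 year and OS 1.5 and 2 years are free of administrative censoring because minimum planned follow-up is 24 months. But they do not settle Pearson against Spearman, and they leave both coefficients open to attenuation. A Cox advantage is also partly built into a simulation that generates proportional hazards.

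Four stronger readings are tempting and are not supported.

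- **That censoring causes the whole loss for both coefficients.** It does so mainly for Pearson. Spearman would be about as far behind Cox with complete data.
- **That eight parameters by two outcomes make a chance finding likely.** Section 10.2.1 speaks of estimating coefficients and sets no test or level. If 16 tests at 5% were imposed, the chance of at least one hit is 14-40% for assumed correlations between parameters of 0.95 down to 0.5. It reaches 1 − 0.95¹⁶ = 56% only if all are independent.
- **That a compliance-OS correlation would almost surely be spurious.** The 92-99% figure needs wear to halve and the device to be worn until death. Section 6.1.2.6.1 ends device use at second progression, at prohibitive deterioration or at 24 months, so earlier stopping is plausible. The documents give no figure for wear decline.
- **That Table 2 treats living participants as deaths.** It says "If the study ends and the participant is still living, OS will be measured in days from Study Day 0" and does not mention censoring. The planned log-rank test and the follow-up statement in section 11.1.9.2 imply censoring, so this is a wording gap only.

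**Conclusion.** The point holds as a should-fix. Two sections commit to different coefficients for one exploratory question, and neither suits censored outcomes. On the plan's own inputs, 13-31% of TTFields-arm OS times are censored. Relative to Cox, Pearson gives up about 8-12 points of power, mostly through censoring, and Spearman about 13-16, mostly for other reasons. The censored shares rest on the plan's Weibull and accrual assumptions. The power figures also rest on an assumed log-hazard of 0.3 per SD and a normally distributed parameter.

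The compliance endpoint is a lesser matter: its status differs between Table 2 and the synopsis, and its analysis is unwritten. The size of any bias from declining wear cannot be established from the documents.

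**What to change.** **Field/SAR.** In both 10.2.1 and 6.3.2.2, replace Pearson and Spearman for OS and PFS with one Cox model per outcome. Enter the baseline-scan parameter as a continuous covariate and report the hazard ratio per SD with a 95% CI. Censor OS at last contact and PFS at last tumour assessment. Naming one lead parameter among the eight before outcomes are linked is advisable. State in Table 2 that living participants are censored.

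**Compliance.** Reconcile the endpoint's status between Table 2 and the synopsis. If it is kept, add to 10.2.1 a landmark Cox model on mean percent use while on device in a fixed early window, with OS counted from a later landmark among patients alive then. Fix window and landmark before compliance and survival data are linked. Data lock is too late in an open-label trial with monthly compliance reports. Report the result as an association.

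**Cost.** A wording amendment with IRB approval and the sponsor and funding-agency agreement in the Statement of Compliance; no new data. The landmark does cost power. For example, take use in months 0-6 with a landmark at month 9, a log-hazard of 0.3 and medians 28 and 22. Power is then 59-64% with steady wear, against 64-71% for a Cox model on whole-treatment average wear, and 7-11% of patients die before the landmark. With an assumed monthly within-patient SD of 0.2, power is 45-47% against 60-66%.
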